2.2 Treatment Assignment

After informed consent has been obtained and the subject's eligibility is established, the subject will be enrolled and a number will be assigned through an interactive voice response system (IVRS). Every subject that signs the informed consent form must be assigned a subject number in IVRS. Once enrolled in IVRS, subjects that have met all eligibility criteria will be ready for treatment and drug vial assignment through the IVRS.

2.3 Blinding and Unblinding

Not applicable.

2.4 Protocol Amendments

This SAP incorporates the following protocol Amendment:

Amendment	Date of Issue	Summary of Major Changes
Revised Protocol 1	18-Jan-2018	
• Changed primary end point from Clinical Benefit Rate at week 16 (CBR16) to Objective Response Rate (ORR).• Statistical analysis is modified to include a pause rule and clarification of final analysis of each bin.• Adverse Events were updated to include Immune-Mediated Adverse Events (IMAEs)• Vital signs were added to follow-up assessments• 28 days screening window removed• Adenocarcinoma of the small bowel and Adrenocortical carcinoma were added to inclusion criteria• Additional tumor types were added to the exclusion criteria• Treatment duration for 24 months
Revised Protocol 2	31-May-2018	
• Incorporated change as per Administrative Letter 03• Updated Medical Monitor information• Added minor changes to statistical section• Added language that Oncology TA was responsible for the design and conduct of the study and decisions regarding the protocol will be made with consultation with the Steering Committee• Added language for early stopping considerations

2.5 Data Monitoring and Other External Committees

There will be no independent Data Monitoring Committee (DMC) in this study. A Steering Committee comprised of trial investigators, trial statisticians, and BMS physicians will be created to design the trial and govern the trial's conduct, scope, and execution. The oncology therapeutic area of BMS has primary responsibility for overall design and conduct of the study. Decisions regarding the study protocol will be made by the sponsor upon consultation with the steering committee.

3 OBJECTIVES

3.1 Primary

To evaluate investigator-assessed Objective Response Rate (ORR) of nivolumab monotherapy in advanced or metastatic malignancies.

3.2 Secondary

- To assess duration of investigator-assessed clinical response (duration of response)
- To assess time to response (TTR)
- To assess clinical benefit rate (CBR)
- To assess overall survival (OS) at 1 year.
- To assess safety of nivolumab in malignancies in this trial.
- To correlate clinical response and OS to programmed death-ligand 1 (PD-L1) expression.
- To correlate clinical response and OS to MisMatch Repair (MMR) alterations.

4 ENDPOINTS

4.1 Primary Endpoint(s)

The primary endpoint of this trial is investigator-assessed ORR of nivolumab monotherapy. ORR is defined as the number of participants with a best overall response of confirmed CR or PR divided by the number of all treated participants. Best overall response is defined as the best response designation, as determined by investigator, recorded between the date of first dose and the date of objectively documented progression per tumor-specific response criteria or the date of subsequent therapy, whichever occurs first. For participants without documented progression or subsequent therapy, all available response designations will contribute to the BOR determination. For subjects who continue treatment beyond progression, the BOR will be determined based on response assessments up to the time of initial RECIST 1.1 progression.

Tumor assessments will occur at Week 8, Week 16, Week 28 and then every 12 weeks until disease progression. BOR for each patient will be derived as one of the following categories:

- Complete response (CR): At least two objective statuses of CR documented with a minimum of 4 weeks apart before progression.
- Partial response (PR): At least one objective status of PR at one visit and then at the subsequent (not need to be second one, any visits after the first 'PR') visit with a CR or PR, and two objective statuses documented with a minimum of 4 weeks apart before progression.
- Stable disease (SD): At least one objective status of stable documented at least 6 weeks after first dosing date and before progression but not qualifying as CR, PR, Or for unconfirmed CR or PR documented at least 6 weeks after first dosing date and before progression.
- Progressive Disease (PD): Objective status of progression and not qualifying as CR, PR or SD.
- Not evaluable (NE).

4.2 Secondary Endpoint(s)

4.2.1 Duration of Response

DOT is defined as the time from first confirmed response (CR or PR) to the date of the first documented tumor progression as determined by investigator or death due to any cause, whichever occurs first. Participants who start subsequent therapy without a prior reported progression will be censored at the last evaluable tumor assessments prior to initiation of the subsequent anticancer therapy. Participants who die without a reported prior progression will be considered to have progressed on the date of their death. Participants who neither progress nor die will be censored on the date of their last evaluable tumor assessment.

4.2.2 TTR

TTR is defined as the time from first dosing date to the date of the first confirmed response, as assessed by investigator.

4.2.3 CBR

CBR is defined as the number of participants with a best overall response of confirmed CR or PR, or stable disease divided by the number of all treated subjects.

4.2.4 Overall Survival

OS is defined as time from the date of first dosing to the date of death. Subjects who did not die by the end of the study will be censored at the last known date alive. OS rate at 1 year is measured as the survival rate at 1 year from Kaplan-Meier curve of OS.

4.2.5 Safety and Tolerability

Safety and tolerability will be measured by the incidence of deaths adverse events (AEs) , serious adverse events (SAEs), adverse events leading to discontinuation, adverse events leading to dose modification, select adverse events (select AEs) leading to dose delay, and specific laboratory abnormalities (worst grade) in each tumor group. Toxicities will be graded using the National Cancer Institute (NCI) Common Terminology Criteria for Adverse Events (CTCAE) version 4.0.

[REDACTED]

[REDACTED]

[REDACTED]

5 SAMPLE SIZE AND POWER

The maximum overall sample size across all tumor groups is 350 subjects. In addition, the maximum permitted sample size per group is 25 subjects, although a group with high posterior probability of success may be permitted a larger sample size at Sponsor discretion. It is expected that accrual may vary across groups, with some groups enrolling a higher number of subjects than other groups within the trial. Simulation studies were conducted to evaluate the performance of the analysis under various assumptions for the distribution of true underlying ORR across the tumor types. Operating characteristics including power and type I error were assessed.

When the treatment effects are similar across all tumor types, estimation efficiencies, due to borrowing, result in strong trial performance. When all groups are in truth effective, the individual groups generally exhibit power between 86.8% and 98.4%, under the scenario of odds ratio improvement of 3. When all groups are ineffective, the individual groups have between a 2.1% and 9.5% chance of mistakenly declaring group success. The group specific type I errors are the metric of interest when evaluating the false positive rate for this type of design. Full presentation and discussion of the simulation parameters, corresponding simulation results, and example trials are included in the Statistical Analysis and Modeling Report provided in the Appendices.

6 STUDY PERIODS, TREATMENT REGIMENS AND POPULATIONS FOR ANALYSES

6.1 Study Periods

6.1.1 Baseline Period

Baseline evaluations or events will be defined as evaluations or events that occur before the date and time of the first dose of study treatment.

In cases where the time (onset time of event or evaluation time and dosing time) is missing or not collected, the following definitions will apply:

- Pre-treatment AEs will be defined as AEs with an onset date prior to but not including the day of the first dose of study treatment

- Baseline evaluations (e.g., laboratory tests and vital signs) will be defined as evaluations with a date on or prior to the day of first dose of study treatment

If there are multiple valid assessments, the assessment that is closest to day (and time if collected) of the first dose of study treatment will be used as the baseline in the analyses. If multiple assessments are collected at the same date (and time if collected), the assessment with the latest database entry date (and time if collected) will be considered as baseline.

6.1.2 Post Baseline Period

On-treatment AEs will be defined as AEs with an onset date and time on or after the date and time of the first dose of study treatment (or with an onset date on or after the day of first dose of study treatment if time is not collected or is missing). An AE will be counted as on-treatment if the event occurred within 30 days (or 100 days depending on analysis) (see Core Safety SAP), of the last dose of study treatment. No subtracting rule will be applied when an AE occurs both pre-treatment and post-treatment with the same preferred term and grade.

On-treatment evaluations (e.g., laboratory tests and vital signs) will be defined as evaluations taken after the day (and time, if collected and not missing) of first dose of study treatment. An evaluation will be counted as on-treatment if it occurred within 30 days (or 100 days depending on analysis) of the last dose of study treatment.

Late emergent drug-related AEs will be defined as drug-related AEs with an onset date greater than 100 days after the last dose of study treatment in subjects off study treatment.

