**Table 5.1-4: Follow-Up Assessments - All Subjects CA209627**

Procedure	Follow-Up Visits X01 (Day 35) ( $\pm 7$ Days) and X02 (Day 100) a ( $\pm 7$ Days) after last dose	Survival Follow-Up Visits b Every 12 weeks	Notes
Safety Assessments			
Targeted Physical Examination	X		Targeted examination must include the Cardiovascular, Gastrointestinal, and Pulmonary body systems and examination to specific malignancy To assess for potential late emergent study drug related findings.
Vital Signs	X	X	
Adverse Events and Serious Adverse Events Assessment	X		All AEs and SAEs must be collected up to 100 days after study drug discontinuation. SAEs that relate to any later protocol specified procedure must be collected.
Review of Medical History and Subsequent Cancer Therapy Information	X	X	
Laboratory Tests	X		CBC with differential, Chemistry panel including LFTs (ALT, AST, total bilirubin, alkaline phosphatase), BUN or serum urea level, creatinine, Ca, Na, K, Cl, phosphate, LDH, and glucose.
Thyroid Function Testing	X		TSH (reflex to free T3 and free T4 if abnormal result)
Pregnancy Test	X		Serum or urine

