**Table 5.1-4: Follow-Up Assessments - All Subjects CA209627**

Procedure	Follow-Up Visits X01 (Day 35) ( $\pm 7$ Days) and X02 (Day 100) a ( $\pm 7$ Days) after last dose	Survival Follow-Up Visits b Every 12 weeks	Notes
Efficacy Assessments			
Radiographic Tumor Assessment	See notes		Only for subjects without progression and no longer on study therapy. If subject starts subsequent treatment, no assessment required  Subjects with a history of brain metastasis may have surveillance MRI approximately every 12 weeks or sooner if clinically indicated
Subject Status			
Survival Status	X	X	Every 3 months after X02; may be accomplished by visit or phone contact, to update survival information and assess subsequent anti-cancer therapy.

NOTES:

a Subjects must be followed for at least 100 days after last dose of study treatment. Follow-up visit #1 occurs approximately 35 days ( $\pm 7$  days) after the last dose or coinciding with the date of discontinuation ( $\pm 7$  days) if date of discontinuation is greater than 30 days after last dose. Follow-up visit #2 occurs approximately 100 days ( $\pm 7$  days) from last dose

b Survival Follow-up visits to occur every 3 months from Follow-up Visit 2. At the time of this request, each subject will be contacted to determine their survival status unless the subject has withdrawn consent for all contact. Vital signs not required if follow-up is performed via telephone contact.

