The following will be summarized by tumor group as worst CTC grade on-treatment per subject and as shift table of worst on-treatment CTC grade compared to baseline CTC grade per subject: hemoglobin (HB), platelets, white blood counts (WBC), absolute neutrophils count (ANC) and lymphocyte count (LYMPH).

The analyses will be conducted using the 300-day safety window and repeated using the 100-day safety window.

A by-subject listing of these laboratory parameters will be provided.

7.6.9.2 *Serum Chemistry*

The following will be summarized by tumor group as worst CTC grade on-treatment per subject and as shift table of worst on-treatment CTC grade compared to baseline CTC grade per subject: ALT, AST, alkaline phosphatase (ALP), total bilirubin and creatinine.

The analyses will be conducted using the 300-day safety window and repeated using the 100-day safety window.

A by-subject listing of these laboratory parameters will be provided.

7.6.9.3 *Electrolytes*

The following will be summarized by tumor group as worst CTC grade on-treatment per subject and as shift table of worst on-treatment CTC grade compared to baseline CTC grade per subject: sodium (high and low), potassium (high and low), calcium (high and low), magnesium (high and low).

The analyses will be conducted using the 30-day safety window and repeated using the 100-day safety window.

A by-subject listing of these laboratory parameters will be provided.

7.6.9.4 *Abnormal Thyroid Function Test*

The number of subjects with the following laboratory abnormalities from on-treatment evaluations will be summarized by tumor group:

- TSH value $>$ ULN and
 - with baseline TSH value \leq ULN
 - at least one FT3/FT4 test value $<$ LLN
- TSH $<$ LLN and
 - with baseline TSH value \geq LLN
 - at least one FT3/FT4 test value $>$ ULN

The analyses will be conducted using the 30-day safety window and repeated using the 100-day safety window.

A by-subject listing of these specific abnormalities will be provided.

7.6.9.5 *Abnormal Hepatic Function Test*

The number of subjects with the following laboratory abnormalities from on-treatment evaluations will be summarized by tumor group:

- ALT or AST $>$ 3 x ULN, $>$ 5 x ULN, $>$ 10 x ULN and $>$ 20 x ULN
- Total bilirubin $>$ 2 x ULN

- Concurrent (within 1 day) ALT or AST $> 3 \times$ ULN and total bilirubin $> 2 \times$ ULN
- Concurrent (within 30 days) ALT or AST $> 3 \times$ ULN and total bilirubin $> 2 \times$ ULN

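### Protocol-compliant laboratory results taken at follow-up visit X02 on Days 101 to 107 fall outside both of the SAP's on-treatment windows

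*SAP*

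**What the plan says.** SAP 6.1.2 defines on-treatment evaluations and names laboratory tests and vital signs as examples. Its upper limit is: "An evaluation will be counted as on-treatment if it occurred within 30 days (or 100 days depending on analysis) of the last dose". Nothing is added for visit tolerance. The same section defines a late-emergent category beyond 100 days, but only for drug-related adverse events.

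Protocol Table 5.1-4 schedules two follow-up visits, X01 at Day 35 and X02 at Day 100 after the last dose, each with a tolerance of 7 days either way. Note a repeats this for the second visit: "Follow-up visit #2 occurs approximately 100 days", again plus or minus 7. The laboratory row is marked for both visits and asks for "CBC with differential, Chemistry panel including LFTs (ALT, AST, total bilirubin, alkaline phosphatase), BUN or serum urea level, creatinine" and further analytes. Thyroid testing has its own row, also marked for both visits. The separate survival follow-up column has no laboratory tests, so X02 is the last scheduled panel.

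SAP 7.6.9.3 (electrolytes), 7.6.9.4 (thyroid) and 7.6.9.5 (hepatic) each state: "The analyses will be conducted using the 30-day safety window and repeated using the 100-day safety window". SAP 7.6.9.1 (hematology) and 7.6.9.2 (serum chemistry) instead state: "The analyses will be conducted using the 300-day safety window and repeated using the 100-day safety window".

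**The concern.** The long window stops at the nominal day of X02, while the protocol lets the visit run a week later. Take two subjects who both follow the protocol, one sampled on Day 100 and one on Day 101. The first enters the 100-day table and the second does not, although nothing about drug exposure separates them. The appointment date decides.

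Protocol 5.3 has toxicity assessed through both safety follow-up visits, so X02 results are collected in order to be used. An electrolyte, thyroid or hepatic abnormality first seen on Days 101 to 107 would be missing from the worst-grade, shift or abnormality counts, and no category for later laboratory values takes it in.

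The two window statements within SAP 7.6.9 add a second problem. ALT, AST and total bilirubin are summarized under both serum chemistry and hepatic function. Read literally, one Day 103 sample would count in the first and not in the second.

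**Working it through.** The documents give no figure on this point, so there is nothing to reproduce. The check is a day count, with days counted from the last dose as in note a to Table 5.1-4.

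**Inputs**
- X01: Day 35 ± 7 (Protocol Table 5.1-4)
- X02: Day 100 ± 7 (same table)
- Cut-offs: 30 and 100 days (SAP 6.1.2 and 7.6.9.3 to 7.6.9.5); 300 and 100 days as printed (SAP 7.6.9.1 and 7.6.9.2)

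**Permitted days**
- X01: 35 − 7 = 28 to 35 + 7 = 42, which is 42 − 28 + 1 = 15 days
- X02: 100 − 7 = 93 to 100 + 7 = 107, which is 107 − 93 + 1 = 15 days

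**Permitted days inside each cut-off**

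| Cut-off | X01 inside | X01 outside | X02 inside | X02 outside |
|---|---|---|---|---|
| 30 days | 3 (Days 28–30) | 12 (Days 31–42), 12/15 = 80% | 0 | 15 |
| 100 days | 15 | 0 | 8 (Days 93–100) | 7 (Days 101–107), 7/15 = 47% |
| 300 days, as printed | 15 | 0 | 15 | 0 |
| 107 days, proposed | 15 | 0 | 15 | 0 |

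**What is outside both windows.** For electrolyte, thyroid and hepatic tables this is X02 on Days 101 to 107 only. X01 on Days 31 to 42 misses the 30-day table but is in the 100-day repeat.

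**From days to subjects.** The documents give no actual visit dates, so the share of compliant X02 panels left out has to be shown as a range:
- all X02 visits on or before Day 100: 0%
- visits spread evenly over Days 93 to 107 (assumption): 7/15 = 47%
- visits spread evenly over Days 100 to 107 (assumption, for sites that treat the 100-day minimum follow-up in note a as the earliest date): 7/8 = 88%
- all X02 visits after Day 100: 100%

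**Effect on one table.** SAP Section 5 normally caps a group at 25 subjects. With all 25 in the denominator, one subject whose only qualifying abnormality is excluded lowers the group's incidence by 1/25 = 4 percentage points, and by more in a smaller group.

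**The case against.** The strongest reply is that this is a modest gap in descriptive tables, and that it is easy to read too much into it. Several parts of that reply stand.

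- **X01.** A reader might infer that X01 results are lost as well, since the nominal Day 35 lies beyond 30 days. They are not: the 100-day repeat includes all of Days 28 to 42. A short and a long view are meant to differ. X01 may also be timed to the discontinuation date "if date of discontinuation is greater than 30 days after last dose", so it is not confined to those days. A Day 42 short window is therefore unnecessary, and a footnote is enough.
- **Scope.** A reader might infer that every worst-grade and shift table is affected. As printed, the 300-day window for hematology and serum chemistry keeps every X02 result. Those tables are affected only if 300 is a misprint for 30.
- **Other routes.** Dropped would be too strong a word. By-subject listings are planned, with no stated cut at these windows. Protocol 6.3 sends clinically significant results, and those that lead to interruption, discontinuation or corrective therapy, to the AE or SAE forms. Protocol 6.6 makes potential drug-induced liver injury an SAE. Drug-related AEs beyond 100 days have their own summary. These are partial backstops: a graded shift that meets none of those conditions appears in no on-treatment summary.
- **Convention.** SAP 7.6 defers to the sponsor's Core Safety SAP where appropriate, and that document is not available here. It may hold visit-window rules. But 6.1.2 states its own cut-off for evaluations, and it points to the Core Safety SAP only in the sentence on adverse events. The explicit rule governs as written.
- **Consistency with AEs.** A longer laboratory window means that a Day 105 value could enter a laboratory table while an AE with that onset date stays outside the 100-day AE table. This is a real cost of the change.

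**Conclusion.** The mismatch holds for X02. Compliant results on Days 101 to 107, 7 of the 15 permitted days, are outside both windows for the electrolyte, thyroid and hepatic summaries. For electrolyte and thyroid values no other laboratory summary takes them in. For ALT, AST and bilirubin the serum chemistry tables would do so only if the 300-day text is literal. That text contradicts 6.1.2 and has to be resolved either way; if 30 was meant, hematology and serum chemistry share the gap.

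A reader might take 47% as the share of subjects or panels lost. The documents do not support that: it is a share of calendar days, and the share of subjects could be anything from 0 to 100%. The conclusion rests on reading 6.1.2 as written, with no unstated visit-window rule in the Core Safety SAP. It concerns descriptive safety tables only. The ORR analysis and the stopping rules are untouched. The change is worth making because it is cheap and removes an arbitrary rule.

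**What to change.** 1. In SAP 6.1.2, for scheduled evaluations (laboratory tests, and vital signs taken at the same visit), end the long window at Day 107, the last permitted day of X02. Keep the standard 100-day table as a supportive display.
2. Reconcile the 300-day text in SAP 7.6.9.1 and 7.6.9.2 with 6.1.2.
3. Footnote the 30-day laboratory tables to say that they mostly exclude X01.
4. Leave the AE windows at 30 and 100 days, since AEs carry their own onset dates.

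The cost is a few lines of SAP text, one programming cut-off and an extra set of supportive tables. Visits and data collection do not change. The downside is a 7-day departure from the sponsor's 100-day convention, with laboratory and AE long windows that differ by 7 days. The supportive 100-day table preserves comparability, and the table titles should state which window applies.

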6.2 Treatment Regimens

Treatment period, Phase 1: Subjects will receive treatment with nivolumab 240 mg as a 30 minute infusion on Day 1 of a treatment cycle every 2 weeks (14 days) for 8 doses until progression, unacceptable toxicity, withdrawal of consent, the study ends, or until Phase 2 dosing begins, whichever occurs first.

Treatment period, Phase 2: Beginning with Dose 9, subjects will receive nivolumab 480 mg as a 30 minute infusion every 4 weeks (\pm 3 days) until progression, unacceptable toxicity, withdrawal of consent, or the study ends, whichever occurs first. Subjects will receive study drug for the maximum treatment duration of 24 months.

